7.4. On study and pre-study closure activities

7.4.1. Data monitoring

In conjunction with the investigators, the Sponsor will constantly monitor the incoming safety data, especially TEAEs, SAEs and SUSARs to continuously assess the overall risk/benefit of the patients enrolled in this study and to take appropriate actions.

The DM review is also intended as data quality check in order to verify the consistency of the data entered and identify any possible misconduct from the site.

Data Safety Committee

A DSC will be established consisting of the Principal Investigator(s) and the Sponsor's qualified medical representative(s), as well as invited experts (such as statistician and pharmacokineticist), as appropriate. The DSC is responsible for reviewing and evaluating all the available safety data, any DLTs and PK data collected during Step 1 in order to confirm the RP2D to be tested in Step 2. During Step 2 of the study, safety and need for dose reductions and/or modifications will continue to be monitored for all patients in all cycles and the DSC will review this study in regular meetings (at least every 3 months).

The DSC may also meet in ad hoc meetings at its discretion, as needed in response to events occurring in the study. Data will be provided by the Sponsor to the DSC as described in the approved Data Review Plan. The Data Review Plan will be finalized under responsibility of the Sponsor before First Patient In.

Roles and responsibilities of the DSC as well as the meeting schedule are provided in a separate DSC Charter.

7.4.2. Protocol Deviations and Data Review Meeting

Categories of protocol violations will be defined and will be integrated in the statistical analysis. A data review meeting (DRM) will take place at the end of the study in order to evaluate and accept the data management report, discuss remaining issues (outstanding queries, unresolved errors) and to confirm and approve relevant protocol violations. After this final DRM has taken place and the database is considered cleaned, the database will be locked.

The Listing of Protocol Deviation categories will be attached to the SAP after the data review meeting, according to the following data structure:

PD Category number	Programmed by DM	Importance	PD Category	PD Subcategory	Description

8. Determination of sample size

[REDACTED]

9. Randomization Methodology

Not Applicable.

10. Stopping Rules and Blinding

10.1. Stopping Rules

No additional rules compared to the ones highlighted in section 5.1.

10.2. Blinding

This is an open-label study; thus, study subjects and investigators will not be blinded to treatment assignment.

An independent review committee, blinded to subjects' treatment assignment, will review radiographic images and clinical information collected on-study to determine the endpoints of disease response and progression.

Unblinded safety data will be reviewed at pre-specified intervals by the Data Safety Committee.

11. Statistical analysis and methods

11.1. Multiplicity adjustment

Not applicable.

11.2. Descriptive statistics

All study variables (with the exception of PK variables) will be presented by dose cohort and

overall, using the appropriate descriptive statistics according to the variable nature, unless otherwise specified:

- **Continuous variables:** Number of non-missing observations, arithmetic mean, standard deviation, minimum, median and maximum.
- **Categorical variables:** Number of non-missing observations and column percentages (N, %).
- **Time to event variables:** Number of non-missing observations, number and percentage of censored observations, 1st quartile, median (and its 95% CI), 3rd quartile, Kaplan-Meier survival curves and event rate every 28 days.

The behaviour over time of study variables will be summarised by treatment cohort and overall as follows:

- **Continuous variables:** Descriptive statistics for each time point and for the absolute/percentage differences to baseline.
- **Categorical variables:** Descriptive statistics for each time point and shift tables to baseline.

Correlation among patient's variables will be evaluated calculating the appropriate correlation coefficient with the respective statistical significance level.

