
Study Duration
 
The overall study duration will depend on the completion of the dose levels/cohorts, the number of patients to be treated per each dose-cohort and the completion of Step 2 up to a total of 40 evaluable patients for efficacy.
 
All patients pre-screened for the PIK3CA mutation will undergo a maximum 4 weeks Screening Period.
 
Each treatment cycle will last 28 days.
 
Individual study duration will depend on the duration of the study treatment which continues up to disease progression or study discontinuation for other reasons.
 
The End of Study Visit will be performed 4 weeks after the last dose of MEN1611.
 
Survival Follow-up:
 
After the End of Study Visit, all patients evaluable for efficacy will be followed for survival status according to local practice (a visit or a telephone call) every 12 weeks up to the End of Study.
 
End of Study:
 
The study ends with the End of Study Visit of the last patient who discontinues the study treatment.
 
For safety monitoring, all serious adverse events (SAEs) with a suspected causal relationship to the study treatment that occur after the End of Study must be recorded and notified to the Sponsor.
	

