 - Dispensing of MEN1611 and administration in fasting condition of the first assigned dose (48 mg or 32 mg as 3 or 2 capsules BID, respectively).

Note-1: Patients will be monitored at the site for occurrence of AE during cetuximab infusion and after the end of infusion for at least 1 hour.

Note-2: An ophthalmic visit shall be performed in case ocular disorders Grade ≥ 2 are assessed (the AE has to be followed until resolution to Grade 1). A dermatological visit shall be performed in case skin toxicity Grade ≥ 3 is assessed (the AE has to be followed until resolution to Grade 1). The frequency of ophthalmic and dermatological visits can be increased upon Investigator's judgement.

Cycle 3 up to Cycle 6:

Visit 1 (Day 1) (+ 5-Day window)

(All assessments can be performed within 48 hours prior to administration of the study treatment at site, unless otherwise indicated.)

- Physical examination including vital signs (i.e. BP, heart rate, respiratory rate, body temperature) and weight.
- Blood samples for haematology, coagulation and chemistry including HbA1c.
- Serum pregnancy test (if applicable).
- Blood sample for central analysis of tumour markers before the treatment: ctDNA levels ONLY at Cycle 3 and CTC enumeration ONLY at Cycle 3 and Cycle 5.
- Tumour assessment using RECIST v1.1 will be performed at Cycle 3 and Cycle 5 (within a window of 7 days before the visit date).
- Sample for urinalysis.
- Assessment of ECOG PS.
- 12-lead ECG (same technique used at baseline) will be performed ONLY at Cycle 3 and Cycle 5.
- Dispensing of the patient diary for study treatment compliance.
- Recording of AEs and concomitant medications.
- Study treatment administration, according to the following order:
 - Premedication with a corticosteroid and a H1 receptor antagonist 30-60 minutes prior to the cetuximab application.
 - Cetuximab 250mg/m² as a 60 minutes IV infusion.
 - Dispensing of MEN1611 and administration in fasting condition of the first assigned dose (48 mg or 32 mg as 3 or 2 capsules BID, respectively).

Note: Patients will be monitored at the site for occurrence of AE during cetuximab infusion and after the end of infusion for at least 1 hour.

Visit 2 (Day 8), Visit 3 (Day 15), Visit 4 (Day 22):

(All assessments can be performed within 48 hours prior to administration of the study treatment at site, unless otherwise indicated.)

- Physical examination including vital signs (i.e. BP, heart rate, respiratory rate, body temperature) and weight.

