- Assessment of ECOG PS.
- Blood samples for haematology, coagulation and chemistry, ONLY at Day 15.
- Recording of AEs and concomitant medications.

- Study treatment administration, according to the following order:
 - Premedication with a corticosteroid and a H1 receptor antagonist 30-60 minutes prior to the cetuximab application.
 - Cetuximab 250mg/m² as a 60 minutes IV infusion.
 - Dispensing of MEN1611 and administration in fasting condition of the first assigned dose (48 mg or 32 mg as 3 or 2 capsules BID, respectively).

Note-1: Patients will be monitored at the site for occurrence of AE during cetuximab infusion and after the end of infusion for at least 1 hour.

Note-2: An ophthalmic visit shall be performed in case ocular disorders Grade ≥ 2 are assessed (the AE has to be followed until resolution to Grade 1). A dermatological visit shall be performed in case skin toxicity Grade ≥ 3 is assessed (the AE has to be followed until resolution to Grade 1). The frequency of ophthalmic and dermatological visits can be increased upon Investigator's judgement.

Cycle 7 Onwards:

Visit 1 (Day 1) (+ 5-Day window), Visit 2 (Day 8), Visit 3 (Day 15) and Visit 4 (Day 22)

(All assessments can be performed within 48 hours prior to administration of the study treatment at site, unless otherwise indicated.)

- Physical examination including vital signs (i.e. BP, heart rate, respiratory rate, body temperature) and weight.
- Assessment of ECOG PS.
- 12-lead ECG (same technique used at baseline) at Day 1 of Cycle 7 and then EVERY 2 cycles.
- Blood samples for haematology, coagulation and chemistry including HbA1c ONLY at Day 1.
- Serum pregnancy test (if applicable) ONLY at Day 1.
- Sample for urinalysis ONLY at Day 1.
- Tumour assessment using RECIST v1.1 at Day 1 of Cycle 7 and then EVERY 2 cycles (within a window of 7 days before the visit date).
- Blood sample for CTC enumeration before the treatment ONLY at Day 1 of Cycle 7 and then EVERY 2 cycles.
- Dispensing of the patient diary for study treatment compliance at Day 1.
- Recording of AEs and concomitant medications.
- Study treatment administration, according to the following order:
 - Premedication with a corticosteroid and a H1 receptor antagonist 30-60 minutes prior to the cetuximab application.
 - Cetuximab 250mg/m² as a 60 minutes IV infusion.

- Dispensing of MEN1611 and administration in fasting condition of the first assigned dose (48 mg or 32 mg as 3 or 2 capsules BID, respectively).

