8.5.5.2 Secondary Endpoints

- Safety and tolerability:
 - Incidence, severity as per CTCAE v. 5.0 grading, seriousness and treatment-causality of TEAEs.
 - Frequency of clinically significant abnormalities in physical examination, safety laboratory tests, urinalysis, vital signs and 12-lead ECG.
- PK profile: MEN1611 plasma concentration-time data will be analysed using a population PK approach. A nonlinear mixed effects model will be used to determine population PK parameters and their associated variabilities (e.g. CL/F, V/F, Ka). Individual PK parameters (e.g. AUC, Cmax) will be estimated using a post hoc analysis.
- Disease Control Rate (DCR) defined as percentage of patients whose disease shrinks or remains stable over a certain time period. DCR is the sum of the complete, partial and stable disease rates according to local assessment.
- Duration of response defined as time from confirmation of a PR, CR or SD as locally assessed, until the disease has been shown to progress following treatment.
- PFS: Defined as the number of days between the first study treatment administration to the date of first documented disease progression as per local assessment, relapse or death from any cause. Responding patients and patients who are lost to follow-up are censored at their last tumour assessment date.
- OS: Defined as the number of days between the first study treatment administration and death from any cause.

For the baseline assessment, CT scan or MRI should be performed no more than 4 weeks before the start of study treatment. Follow-up assessment will be performed every 2 cycles during study treatment starting from Day 1 Cycle 3 (within a window of 7 days before the visit date) until objective disease progression as defined by RECIST v1.1 or at the End of Study Visit. Any other site at which a new disease is suspected should be appropriately imaged. If an unscheduled assessment is performed and the disease has not progressed, subsequent assessments should be performed at their scheduled visits.

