For the baseline assessment, CT scan or MRI should be performed no more than 4 weeks before the start of study treatment. Follow-up assessment will be performed every 2 cycles during study treatment starting from Day 1 Cycle 3 (within a window of 7 days before the visit date) until objective disease progression as defined by RECIST v1.1 or at the End of Study Visit. Any other site at which a new disease is suspected should be appropriately imaged. If an unscheduled assessment is performed and the disease has not progressed, subsequent assessments should be performed at their scheduled visits.

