12.1. Efficacy analysis

The following parameters will be summarized by cohort and overall (if appropriate) on the Efficacy population:

- Best Overall Response
- Disease Control Rate
- Objective Response Rate
- Duration of response (DoR)
- Progression Free survival (PFS);
- Overall Survival (OS).

ORR locally assessed is the primary endpoint of the Cohort Expansion Phase. All efficacy

endpoints related to tumour assessment will be evaluated considering both local (secondary endpoints) and central (exploratory endpoints) radiology assessments.

Best Overall Response (BOR) is derived as follows:

- If a subject has at least one overall response of CR, then BOR is CR;
- If a subject doesn't have any overall response of CR but has at least one overall response of PR, then BOR is PR;
- If a subject doesn't have any overall response of CR or PR but has at least one overall response of SD (or Non-CR / Non-PD) at least six weeks after the first intake of MEN1611, then BOR is SD (or Non CR / Non PD);
- If a subject doesn't have any overall response of CR, PR, SD (or Non-CR / Non-PD) after at least 6 weeks from the first intake of MEN1611, but has at least one overall response of PD, then BOR is PD;
- In all other cases, BOR is NE.

Objective Response Rate (ORR) is calculated as the sum of BOR rates of complete response (CR), partial response (PR).

Disease Control Rate (DCR) is calculated as the sum of BOR rates of complete response (CR), partial response (PR) and stable disease (SD).

Overall Survival (OS) is calculated as:

- In case of all-cause death:
OS = date of death - date of first study treatment administration + 1;
- In case of censored information not for drop-out:
OS = date of end of observation period (i.e. maximum between end of study and last follow up date) - date of first study treatment administration + 1;
- In case of censored information for drop-out:
OS = last available date in eCRF - date of first study treatment administration + 1.

Progression-free Survival (PFS) is calculated as:

- In case of death/disease progression:
PFS = date of death or date of first disease progression - date of first study treatment administration + 1
For subjects who experienced both death and progression disease, the date referred to the event that came first is considered.
- In case of censored information due to responding subjects or lost to follow-up:
PFS = date of censoring - date of first study treatment administration + 1

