Detailed censoring rules are as follows:

Circumstances		Options for end-date (progression or censoring)	Outcome
1	Documented Progression	(i) Date of documented progression	Progressed
2	Death without documented progression	(i) Date of death	Progressed
3	Documented progression or death after exactly one missing assessment	(i) Date of progression or death	Progressed
4	Documented progression or death after two or more missing assessments	(i) Date of last adequate assessment ^a	Censored
5	No documented progression and no death (with at least one post baseline assessment)	(i) Date of last adequate assessment	Censored
6	Treatment discontinuation Reason ' Disease progression/clinical progression/progression ' without radiological assessment.	(i) Ignore clinical progression and follow situations above	As per above circumstances
7	No baseline tumor assessment	Date of first study treatment administration	Censored
8	No post baseline assessment and no death	Date of first study treatment administration	Censored
9	Subject lost to follow-up (or withdrew consent) before documented progression or death	(i) Date of last adequate assessment	Censored

^aAfter the last adequate tumor assessment. Date of next scheduled assessment- as specified in the protocol

Duration of Response (DR) is calculated as:

- In case of disease progression:
DR = date of disease progression – date of first occurrence of a BOR of PR, CR or SD + 1
- In case of censored information:
DR = date of last tumor assessment – date of first occurrence of a BOR of PR, CR or SD + 1

Note: subjects with only one assessment post baseline with response equal to PD won't be counted for the DR calculation

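### The 28-day Kaplan-Meier grid reads PFS and duration of response inside the scan windows, so rates at Days 56, 112 and 168 depend partly on the booked scan day

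*SAP*

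**What the plan says.** SAP 11.2 lists the summaries for time-to-event variables, including "Kaplan-Meier survival curves and event rate every 28 days". Protocol 9.3.1 has the same text. It covers PFS, duration of response (DoR) and OS alike.

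The scan calendar follows the cycles. The Protocol synopsis states: "Each treatment cycle will last 28 days". Protocol 8.5.5.2 and SAP 5.4.2 place scans every 2 cycles from Day 1 of Cycle 3, "within a window of 7 days before the visit date". From Cycle 2 on, the visit itself may be late: Protocol 8.5.1 gives "Visit 1 (Day 1) (+ 5-Day window").

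The time scale is set in SAP 12.1: "PFS = date of death or date of first disease progression - date of first study treatment administration + 1". The censoring table there gives a progression its actual date ("i) Date of documented progression"). DoR is also a date difference plus 1, counted from the first scan showing the best response of CR, PR or SD.

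No rule in the SAP maps scans to nominal days, treats progression as interval-censored, or moves the landmarks away from the scan windows. SAP 11.3 handles missing scan dates and a last scan entered as unscheduled, but does not place scans on nominal days.

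**The concern.** Apart from deaths, PFS events are found at scans, so a PFS curve drops mainly during the scan windows and is nearly flat between them. A rate read between windows is insensitive to the exact scan day. A rate read inside a window counts the progressors scanned so far and leaves out those whose appointment fell a day or more later, although their disease may be the same.

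Both the reading grid and the cycle are 28 days long. From Day 56 on, every second reading therefore lands in a scan window. In a single-arm descriptive analysis the tabulated rates are themselves the reported result, so a landmark that moves with appointment dates can mislead whoever reads the table.

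**Working it through.** **1. Scan days on the SAP scale.** Day 1 of cycle c falls on PFS day 28(c − 1) + 1. The scan may be up to 7 days earlier. A single late visit adds up to 5 days. The grid reads at 28(c − 1).

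| Scan | Nominal day | 7-day window | With one +5-day visit, no cycle delay | Landmark |
|---|---|---|---|---|
| Cycle 3 Day 1 | 2×28 + 1 = 57 | 50-57 | 50-62 | 56 |
| Cycle 5 Day 1 | 4×28 + 1 = 113 | 106-113 | 106-118 | 112 |
| Cycle 7 Day 1 | 6×28 + 1 = 169 | 162-169 | 162-174 | 168 |

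Each landmark lies in a window, one day before the nominal scan day. Days 28, 84 and 140 lie in no window. Day 84 is 84 − 62 = 22 days after the latest undelayed first scan.

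**2. Size for PFS.** The plan states no landmark rate to reproduce, so this is an illustration. Inputs:
- n = 40, the number of evaluable patients in the Protocol synopsis.
- k = 18 progressing at the first scan. This is an assumption: 43.8% had progressive disease in the cetuximab-plus-oxaliplatin rechallenge study cited in Protocol 6.2, and 0.438 × 40 = 17.5.
- f = share of first scans dated on or before Day 56.
- No deaths or censoring before the landmark.

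Then PFS(56) = 1 − k·f/n.

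| Booking of first scan | f | k = 12 | k = 18 | k = 22 |
|---|---|---|---|---|
| All on Day 57 or later | 0 | 100% | 100% | 100% |
| Half by Day 56 | 1/2 | 85.0% | 77.5% | 72.5% |
| Uniform over Days 50-57 | 7/8 | 73.8% | 60.6% | 51.9% |
| All by Day 56 | 1 | 70.0% | 55.0% | 45.0% |

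If bookings were uniform over Days 50-62 instead, f = 7/13 and k = 18 gives 1 − 18 × (7/13)/40 = 75.8%. With no further events between scans, the Day-84 rate is 1 − k/n in every row: 70.0%, 55.0% and 45.0% for the three values of k.

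**3. DoR.** For a response first seen at the Cycle 3 scan and progression at the Cycle 5 scan, on-schedule dates give 113 − 57 + 1 = 57. With both scans in their 7-day windows the range is 106 − 57 + 1 = 50 to 113 − 50 + 1 = 64, which straddles Day 56. Write the scans as 57 − b and 113 − a, with a and b each from 0 to 7. Then DoR = 57 − a + b, which is at most 56 when a > b. That holds for 28 of the 64 pairs. If both days are independent and uniform, 44% of these progressions count by Day 56 and 56% do not. Day 84 is outside the range.

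**4. Dependence on the +1.** Protocol 8.5.5.2 defines PFS as a number of days between two dates. Read without the +1, the nominal scan days become 56, 112 and 168 and the windows 49-56, 105-112 and 161-168. The landmarks then sit on the last day of each window, and late visits still fall after them.

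**The case against.** The strongest reply is that nothing is decided on these rates. SAP 12 makes efficacy descriptive with no hypothesis test, and the Step 2 primary endpoint is ORR. The SAP already plans quartiles, medians and full curves, and Days 84, 140 and 196 are already on the grid. On this view the remedy only deletes rows, and a footnote giving the scan schedule would help almost as much. This stands as a limit on importance. It does not make the even-multiple rows sound.

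The 100% figure needs every scan to fall on one side of Day 56. The more ordinary case, uniform over Days 50-57, differs from the all-early case by 60.6 − 55.0 = 5.6 points. That is fair: the extremes are bounds, and k is an assumption rather than a first-scan progression rate from this trial.

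The Efficacy population (SAP 7.3) requires 2 complete cycles, and progression ends treatment (Protocol 8.2.3.2). A patient who progresses on an early-window scan may leave the population instead of counting as an event. This qualifies the figures in the table. It is also another way in which the result can depend on the booked day.

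Two stronger readings are tempting:
- A reader might infer that the affected rates cannot be compared across sites or with external rechallenge data. No such comparison is planned: results are by dose cohort and overall, SAP 12.2 plans no subgroup analyses, and the rechallenge results in Protocol 6.2 are response and control rates, median PFS and OS, not landmark PFS rates.
- A reader might infer that Day 84 is the same in every case. That assumes cycles run close to schedule. If two delays of 21 days each shifted the calendar, Cycle 3 Day 1 would be 57 + 42 = Day 99. If 5 days accrued at each of Cycles 2 to 7, Cycle 7 Day 1 would be 169 + 30 = Day 199, with a window (192-199) that contains Day 196. The MEN1611 dose-modification text is not visible in the public protocol, so how far cycles can shift cannot be settled here. Unscheduled scans are also allowed.

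**Conclusion.** The point holds for PFS and DoR. The plan as written reads PFS at Days 56, 112 and 168 inside the scan windows, and DoR for progression at the next scan straddles Day 56. These rates therefore depend partly on the day the scan was booked.

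With 18 of 40 progressing at the first scan, Day-56 PFS can lie anywhere from 100% to 55.0% for identical disease, with 60.6% under uniform booking over Days 50-57. Day-84 PFS is 55.0% throughout if cycles are not substantially delayed. These figures assume no deaths or censoring before the landmark and no loss from the Efficacy population.

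It would go too far to say that the affected rows measure only booking and nothing of the disease: under most booking patterns they carry both. The primary ORR, the definition of the medians and OS are not affected, and no decision rule changes. This is a worthwhile correction to secondary reporting.

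**What to change.** In SAP 11.2, state that Kaplan-Meier rates for PFS and DoR are reported at times between scan windows: Days 84, 140, 196 and every 56 days after. Keep the 28-day grid for OS, where events are not found by scan. List the departure from Protocol 9.3.1 in SAP 3.1, which at present names the PK analysis as the only exception. Protocol 9.5 calls for a substantial amendment when the primary endpoint or primary analyses change, and this touches neither.

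The cost is one sentence in SAP 11.2, one entry in SAP 3.1 and a changed list of times in the program behind the time-to-event table. No new data are needed. The drawbacks are fewer landmark rows, and that accumulated cycle delays can still bring later landmarks into a scan window.
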